12. PROCEDURE FOR HANDLING PRODUCT QUALITY COMPLAINTS

A Product Quality Complaint (PQC) refers to any written, electronic, or oral communication that alleges deficiencies related to the identity, quality, durability, reliability, safety, effectiveness or performance of test articles after they have been released for clinical trial use.

Potential complaints may come from a variety of sources including but not limited to subjects, clinical research associates (CRA), clinical operations managers (COM), medical monitors, and site personnel, etc. The following are not considered product quality complaints:

- Subject satisfaction inquiries reported via “Subjective Questionnaires” and “Patient Reported Outcomes (PRO)”.
- Clinical test articles that are stored improperly or damaged after receipt at the investigational site.
- Lens replacements that occur due to drops/fall-outs.
- Damage deemed by clinicians or clinical staff to be caused by handling by the user, and not indicative of a quality deficiency (i.e. tears, rips, etc.), only in situations where there is no deficiency alleged by the subject.

Within 24 hours of site personnel becoming aware that a PQC has occurred, the PQC must be recorded in the EDC system, which will trigger an automatic email notification to the appropriate COM/CRA and Clinical QA representative. In cases where the EDC system in use is not configured to send automatic notifications or when an EDC system is not used, the COM/CRA is responsible for notifying Clinical QA upon discovery that a PQC has occurred.

Upon receipt of the EDC notification, the COM/CRA will contact the study site to collect additional information which will include:

- Date the complaint was received/recorded in the EDC System (Date of Sponsor Awareness)
- Who received the complaint

- Study number
- Clinical site information (contact name, site ID, telephone number)
- Lot number(s)
- Unique Subject Identifier(s)
- Indication of who first observed complaint (site personnel or subject)
- OD/OS indication, along with whether or not the lens was inserted
- Any related AE number if applicable
- Detailed complaint description (scheduled/unscheduled visit, wear time, symptoms, resolution of symptoms, etc.)
- Eye Care Provider objective (slit lamp) findings if applicable
- Confirmation of product availability for return (and tracking information, if available), or rationale if product is not available for return [REDACTED]

Once a complaint is received, it will be assessed by the COM, CRA, or trained site personnel to determine if it is an Adverse Event/Serious Adverse Event (AE/SAE). If the complaint results in an AE/SAE, the COM/CRA, or trained site personnel will follow Section 13 of this protocol. If the AE/SAE was potentially the result of a product quality related deficiency, these procedures also applies and will be executed in parallel.

In some cases, a PQC form may be generated in EDC by the site in error. In this event, the PQC forms will be marked “Intentionally Left Blank” or “ILB”. Justification for ILB must be documented.

13. ADVERSE EVENTS

13.1. Definitions and Classifications

Adverse Event (AE) – An AE is any untoward (unwanted) medical occurrence in a patient or clinical investigation subject administered a test article, study treatment or study procedure whether or not caused by the test article, study treatment or procedure. An AE can therefore be any unfavorable or unintended sign (including an abnormal finding), symptom, or disease temporally associated with the use of the test article, study treatment, or study procedure whether or not related to the test article, study treatment, or study procedure.

An AE includes any condition (including a pre-existing condition) that:

1. Was not present prior to the study, but appeared or reappeared following initiation of the study
2. Was present prior to the study, but worsened during the study. This would include any condition resulting from concomitant illnesses, reactions to concomitant medications, or progression of disease states
3. Pregnancy must be documented as an adverse event and must be reported to the clinical monitor and to the Sponsor immediately upon learning of the event

Serious Adverse Event (SAE) – An SAE is any untoward medical occurrence that:

- Results in death
- Is life threatening
- Requires in-patient hospitalisation or prolongation of existing hospitalisation

- Results in persistent or significant disability/incapacity (e.g., a sight threatening event, a significant persistent or permanent change, impairment, damage, or disruption to the subject's body)
- Is a congenital anomaly/birth defect, or
- Requires intervention to prevent permanent damage (the use of the test article resulting in a condition which requires medical or surgical intervention to preclude permanent impairment of the body structure or a body function). Important medical events that may not result in death, be life-threatening, or require hospitalisation may be considered an SAE when, based upon appropriate medical judgment, they may jeopardise the patient or subject and may require medical or surgical intervention to prevent one of the outcomes listed in the above definition.

Diagnoses and conditions that are considered Ocular Serious Adverse Events include, but not limited to:

- Microbial Keratitis (MK)
- Iritis (including cells in the anterior chamber)
- Permanent decrease in best spectacle corrected visual acuity equivalent to 2 acuity lines or greater
- Central Corneal Opacity
- Central Corneal Neovascularisation
- Uveitis
- Endophthalmitis
- Hypopyon
- Hyphema
- Penetration of Bowman's Membrane
- Persistent Epithelial Defect
- Limbal cell Damage leading to Conjunctivalisation

Significant Adverse Events – Those events that are usually symptomatic and warrant discontinuation (temporary or permanent) of the test article (excluding Serious Adverse Events).

Diagnoses and conditions that are considered Ocular Significant Adverse Events include, but not limited to the following:

- Contact Lens Induced Peripheral Ulcer (CLPU)
- Significant Infiltrative Events (SIE)
- Superior Epithelial Arcuate Lesions (SEALs)
- Any Temporary Loss of > 2 Lines of BSCVA
- Other grade 3 or higher corneal findings, such as abrasions or edema
- Non-contact lens related corneal events - e.g. Epidemic Keratoconjunctivitis (EKC)
- Asymptomatic Corneal Scar
- Any corneal event which necessitates temporary lens discontinuation > 2 weeks

Non-Significant Adverse Events – Those conditions that are usually asymptomatic and usually do not warrant discontinuation (temporary or permanent) of the test article. However, the Investigator may choose to treat as a precautionary measure.

Diagnoses and conditions that are considered Ocular Non-Significant Adverse Events include, but not limited to the following:

- Non-significant Infiltrative Event (NSIE)
- Contact Lens Papillary Conjunctivitis (CLPC)
- Superficial Punctate Keratitis (SPK)
- Conjunctivitis: Bacterial, Viral, Allergic
- Blepharitis
- Meibomianitis
- Contact Dermatitis
- Localised Allergic Reactions
- Any corneal event not explicitly defined as serious or significant adverse event, which necessitates temporary lens discontinuation < 2 weeks

Adverse Device Effect (ADE) – A sub-set of AEs, and include only those adverse events that are cause by or related to the investigational device.

Unanticipated Adverse Device Effect (UADE) – Any serious adverse effect on health or safety or any life-threatening problem or death caused by, or associated with, the test article, if that effect, problem, or death was not previously identified in nature, severity, or degree of incidence in the investigational plan, Investigator’s Brochure or protocol, or any other unanticipated serious problem associated with the test article that relates to the rights, safety and welfare of subjects.

13.2. Assessing Adverse Events

In conjunction with the medical monitor, the Investigator will evaluate adverse events to ensure the events are categorised correctly. Elements of categorisation will include:

- Seriousness/Classifications (see definition in Section 13.1)
- Causality or Relatedness – i.e. the relationship between the test article, study treatment or study procedures and the adverse event (not related; doubtful; possible; probable; very likely - see definition in Section 13.2.1)
- Adverse Event Severity – Adverse event severity is used to assess the degree of intensity of the adverse event (mild; moderate; severe for all events - see definition in Section 13.2.2).
- Outcome – Not Recovered or Not Resolved; Recovering or Resolving; Recovered or Resolved with Sequelae; Recovered or Resolved; Death Related to Adverse Event; Unknown
- Actions Taken – None; temporarily discontinued; permanently discontinued; other action taken

13.2.1 Causality Assessment

Causality Assessment – A determination of the relationship between an adverse event and the test article, study treatment, or study procedure. The test article, study treatment or study procedure relationship for each adverse event shall be determined by the Investigator using these explanations:

- Not Related- An adverse event that is not related to the use of the test article, study treatment or study procedures.

- Unlikely Related – An adverse event for which an alternative explanation is more likely, e.g. concomitant treatment, concomitant disease(s), or the relationship of time suggests that a causal relationship is not likely.
- Possibly Related – An adverse event that might be due to the use of the test article, or to the study treatment or study procedures. An alternative explanation, e.g. concomitant treatment, concomitant disease(s), is inconclusive. The relationship in time is reasonable. Therefore, the causal relationship cannot be excluded.
- Related – An adverse event that is listed as a possible adverse effect (device) or adverse reaction (drug) and cannot be reasonably explained by an alternative explanation, e.g. concomitant treatment of concomitant disease(s). The relationship in time is very suggestive, e.g. it is confirmed by de-challenge and re-challenge.

13.2.2 Severity Assessment

Severity Assessment – A qualitative assessment of the degree of intensity of an adverse event as determined by the Investigator or reported to him/her by the subject. The assessment of severity is made irrespective of test article, study treatment or study procedure relationship or seriousness of the event and should be evaluated according to the following scale:

- Mild – Event is noticeable to the subject, but is easily tolerated and does not interfere with the subject’s daily activities
- Moderate – Event is bothersome, possibly requiring additional therapy, and may interfere with the subject’s daily activities
- Severe – Event is intolerable, necessitates additional therapy or alteration of therapy and interferes with the subject’s daily activities

13.3. Documentation and Follow-Up of Adverse Events

The recording and documenting of adverse events (ocular and non-ocular) begins when the subjects are exposed to the test article, study treatment or study procedure. Adverse events reported before the use of test article, start of study treatment, or study procedures will be recorded as medical history. However, if the condition deteriorates at any time during the study it will be recorded and reported as an AE. Untoward medical events reported after the subject’s exit from the study will be recorded as adverse events at the discretion of the Investigator.

Upon finding an adverse event, the Principal Investigator will document the condition in the subject record and in the eCRFs. He/she will complete the Adverse Event /eCRF.

Complete descriptions of all adverse events must be available in the subject record. All Adverse Events including local and systemic reactions not meeting the criteria for “serious adverse events” shall be captured on the appropriate case report form or electronic data system. All adverse events occurring while the subject is enrolled in the study must be documented appropriately regardless of relationship.

It is the Investigator’s responsibility to maintain documentation of each reported adverse event. All adverse events will be followed in accordance with applicable licensing requirements. Such documentation will include the following:

- Adverse event (diagnosis not symptom)
- Drawings or photographs (where appropriate) that detail the finding (e.g., size, location, and depth, etc.)
- Date the clinical site was notified
- Date and time of onset
- Date and time of resolution
- Adverse event classification, severity, and relationship to test articles, as applicable
- Treatment regimen instituted, including concomitant medications prescribed, in accordance with applicable licensing requirements
- Any referral to another health care provider if needed
- Outcome, ocular damage (if any)
- Likely etiology
- Best corrected visual acuity at the discovery of the event and upon conclusion of the event

In addition, if an infiltrate(s) is present, he/she will complete the Corneal Infiltrate Assessment /eCRF. Where necessary, a culture of the corneal lesion will be collected to determine if the infection is microbial in nature. If cultures are collected, the date of culture collection and laboratory utilised will be recorded.

Changes in the severity of an AE shall be documented to allow an assessment of the duration of the event at each level of intensity to be performed. Adverse events characterised as intermittent require documentation of the onset and duration of each episode. Changes in the assessment of relationship to the test article shall also be clearly documented.

Subjects who present with an adverse event shall be followed by the Investigator, within licensure, until all signs and symptoms have returned to pre-treatment status, stabilised, or been satisfactorily resolved. If further treatment beyond licensure is required, the patient will be referred to the appropriate health care provider. The Investigator will use his/her clinical judgment as to whether or not a subject reporting with an adverse event will continue in the study. If a subject is discontinued from the study, it will be the responsibility of the Investigator to record the reason for discontinuation. The Investigator will also document the adverse event appropriately and complete the Adverse Event /eCRF. Any subjects with ongoing adverse events related to the test article, study treatment or study procedures, as of the final study visit date should be followed to resolution of the adverse event or until referral to an appropriate health care provider, as recommended by the Investigator.

13.4. Reporting Adverse Events

The Investigator will notify the Sponsor of an adverse event by e-mail, facsimile, or telephone as soon as possible and no later than 24 hours from discovery for any serious /significant adverse events, and 2 days from discovery for any non-significant adverse event. In addition, a written report will be submitted by the Principal Investigator to the IEC/IRB according to their requirements (Section 13.4.2). The report will comment whether or not the adverse event was considered to be related to the test article, study treatment or study procedures.

13.4.1 Reporting Adverse Events to Sponsor

Serious/Significant Adverse Events

The Investigator will inform the sponsor of all serious/significant adverse events occurring during the study period as soon as possible by e-mail, fax, or telephone, but no later than 24 hours following discovery of the event. The Investigator is obligated to pursue and obtain information requested by the Sponsor in addition to that information reported on the eCRF. All subjects experiencing a serious/significant adverse event must be followed up and all outcomes must be reported.

When medically necessary, the Investigator may break the randomisation code to determine the identity of the treatment that the subject received. The Sponsor and study monitor should be notified prior to unmasking the test articles.

In the event of a serious/significant adverse event, the Investigator must:

- Notify the Sponsor immediately
- Obtain and maintain in the subject's records all pertinent medical information and medical judgment for colleagues who assisted in the treatment and follow-up of the subject
- Provide the Sponsor with a complete case history which includes a statement as to whether the event was or was not related to the use of the test article
- Notify the IEC/IRB as required by the IEC/IRB reporting procedure according to national regulations

Unanticipated (Serious) Adverse Device Effect (UADE)

In the event of an Unanticipated (Serious) Adverse Device Effect (UADE), the Investigator will submit a report of the UADE to the Sponsor and IEC/IRB as soon as possible, but no later than 24 hours after the Investigator first learns of the effect. This report is in addition to the immediate notification mentioned above.

The Sponsor must conduct an evaluation of the UADE and must report the results of the evaluation to FDA, the IEC/IRB and participating Investigators within 10 working days after the Sponsor first receives notification of the effect.

Non-Serious Adverse Events

All non-serious adverse events, including non-serious adverse device effects, will be reported to the sponsor by the Investigator no later than 2 days from discovery.

13.4.2 Reporting Adverse Events to the Responsible IEC/IRB and Health Authorities

Adverse events that meet the IEC/IRB requirements for reporting must be reported within the IEC/IRB's written guidelines. Each clinical site will refer to and follow any guidelines set forth by their Approving IEC/IRB. Each clinical site will refer to and follow any guidelines set forth by their local governing Health Authorities.

The Sponsor will report applicable Adverse Events to the local health authorities according the written guidelines, including reporting timelines.

13.5. Event of Special Interest

None.

13.6. Reporting of Pregnancy

Subjects reporting pregnancy (by self-report) during the course of the study will be discontinued after the event is recorded as an Adverse Event. Once discontinued, pregnant participants and their fetuses will not be monitored for study related purposes. At the Investigator's discretion, the study participant may be followed by the Investigator through delivery. However, this data will not be collected as part of the clinical study database. Pregnant participants are not discontinued from contact lens or solution related studies for safety concerns, but due to general concerns relating to pregnancy and contact lens use. Specifically, pregnant women are discontinued due to fluctuations in refractive error and/or visual acuity that occur secondary to systemic hormonal changes, and not due to unforeseen health risks to the mother or fetus.

14. STATISTICAL METHODS

14.1. General Considerations

Statistical Analysis will be undertaken by the sponsor or under the authority of the sponsor. A general description of the statistical methods to be implemented in this clinical trial is outlined below.

All data summaries and statistical analyses will be performed using the SAS software Version 9.4 or higher (SAS Institute, Cary, NC). Throughout the analysis of data, the results for each subject/eye will be used when available for summarisation and statistical analysis. Unscheduled visits will be summarised separately and will be excluded from the statistical analysis.

Summary tables (descriptive statistics and/or frequency tables) will be provided for all baseline variables, efficacy variables and safety variables as appropriate. Continuous variables will be summarised with descriptive statistics (n, mean, standard deviation (SD), median, minimum and maximum). Frequency count and percentage of subjects or eyes within each category will be provided for categorical data. Unscheduled visits will be summarised separately if applicable.

14.2. Sample Size Justification

[REDACTED]

The sample size was estimated from the formula given by Diggle et al. (2002) for clustered binary data. The common correlation across measurements within subject eyes across period was assumed to be 0.5.

Assuming difference in proportion of 10%, 15%, 20%, the sample size calculation was as shown below:

Difference in Proportion	Number of Subjects needed by study arms
10%	88
12%	70
14%	53
15%	47

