2.3. Hypotheses

Both primary hypotheses must be met in order to satisfy the objectives of this study.

Primary Study Hypotheses	
1	The overall fit acceptance of ACUVUE® OASYS 1·Day will be non-inferior to that of 1·Day ACUVUE® TruEye® of similar base curve. A non-inferiority bound of 1.6 will be used for the odds ratio.
2	The lens power requirement for ACUVUE® OASYS 1·Day will be the same as that of 1·Day ACUVUE® TruEye® in at least 70% of cases and within ± 0.25 D for at least 80% of cases.
Secondary Study Hypotheses	
1	The short-term comfort of ACUVUE® OASYS 1·Day will be non-inferior to that of 1·Day ACUVUE® TruEye® of similar base curve. A non-inferiority bound of 1.0 (0-10 scale) will be used.
2	The subjective vision quality of ACUVUE® OASYS 1·Day will be non-inferior to that of 1·Day ACUVUE® TruEye® of similar base curve. A non-inferiority bound of 10 (0-100 scale) will be used.
3	Monocular high contrast visual acuity with ACUVUE® OASYS 1·Day will be non-inferior to that of 1·Day ACUVUE® TruEye® of similar base curve. A non-inferiority bound of 0.1 logMAR will be used.
4	The handling performance of ACUVUE® OASYS 1·Day will be non-inferior to that of 1·Day ACUVUE® TruEye® of similar base curve. A non-inferiority bound of 1 (0-10 scale) will be used.

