4.3. Enrolment Target and Study Duration

Approximately 45-60 subjects will be enrolled across two sites (15-30 subjects per site) to ensure that at least 43 subjects will complete the study. Enrolled subjects will be habitual wearers of spherical contact lenses. All subjects will be between 18 and 55 years of age. Subjects will be considered enrolled after signing the informed consent. Subjects will wear the Test and Control contact lenses for approximately 45 minutes each for a total study duration of approximately 3 hours per subject.

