14.4. Level of Statistical Significance

All planned analysis for this study will be conducted with an overall type I error rate of 5%. No adjustment for multiple comparisons will be conducted unless specified otherwise.

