14.5. Primary Analysis

All analyses will be conducted on the analysis population (defined above). If the difference between the analysis and safety populations is higher than 15% then a sensitivity analysis will be conducted on all available data.

Primary Endpoints – Overall Fit Acceptance: Overall lens fit acceptability will be analysed using a generalised linear mixed model with a multinomial distribution and a cumulative logit link function. Sequence of lens wear, base curve, period, lens type, site, and the two-way interactions between lens type and base curve and between lens type and period will be included in each model as fixed effects. An appropriate covariance structure will be used to model the residual errors between measurements within same subject across study periods. The covariance structure will be selected based on the finite-sample corrected Akaike’s Information Criterion. Covariance structures considered include:

- Unstructured Covariance Structure (UN)
- Homogenous Compound symmetry (CS)

The Kenward and Roger method⁴ will be used for the denominator degree of freedom. If convergence is problematic, then reduced versions of the above model may be considered.

Comparisons between the Test lens and the control lens will be carried out using two-sided 95% confidence intervals constructed for odds ratio (Test/Control) by base curve. The lower limits of the 95% confidence intervals will be compared to 1.6 and 1 to Test for non-inferiority and superiority, respectively. Non-inferiority of the Test lens relative to the control will be concluded if the upper limit is below 1.6. The superiority will be established if the upper limit is below 1.

Primary Endpoints – Lens Power Requirement: The difference in lens power requirement between the Test and Control lenses will be calculated by base curve for the purpose of the analyses. The proportions, and the corresponding 95% confidence intervals, of eyes with no difference in lens power requirement and with a difference within ± 0.25 D will be calculated. The 95% two-sided confidence intervals of the proportions will be calculated using the method of Wilson.³ The lower limits of the confidence intervals will be compared to 70% and 80%. Equivalence will be established if the lower limit of the proportion with no differences is above 70% and if the lower limit of the proportion within ± 0.25 D is above 80%.

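### The visible sample-size basis in 14.2 (differences in binary proportions) does not match the fit test in 14.5 (ordinal odds ratio, bound 1.6), and the rows that 45–60 subjects reach are looser than that bound

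*Combined protocol and SAP*

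**What the plan says.** **Sample size (14.2).** After a redacted block, the text reads "The sample size was estimated from the formula given by Diggle et al. (2002) for clustered binary data". It assumes a correlation of 0.5 within eyes across periods. The table then gives 88, 70, 53 and 47 subjects for differences in proportion of 10%, 12%, 14% and 15%. The visible text mentions no odds ratio, no ordinal grade and no non-inferiority bound.

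**Enrolment (4.3).** "Approximately 45-60 subjects will be enrolled across two sites (15-30 subjects per site) to ensure that at least 43 subjects will complete the study".

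**Fit hypothesis and test (2.2, 2.3, 14.5).** Fit is an investigator grade from 0 to 5, analysed with a cumulative-logit mixed model. Section 2.3 says: "A non-inferiority bound of 1.6 will be used for the odds ratio". Section 14.5 uses "two-sided 95% confidence intervals constructed for odds ratio (Test/Control) by base curve" and decides as follows: "Non-inferiority of the Test lens relative to the control will be concluded if the upper limit is below 1.6".

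**Role of the fit hypothesis (2.3).** "Both primary hypotheses must be met in order to satisfy the objectives of this study". The second primary hypothesis concerns lens power requirement and is stated as proportions with thresholds of 70% and 80%.

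**The concern.** The calculation that supports N and the test that N must support differ in three ways: scale (difference in proportions against odds ratio), outcome (binary against ordinal) and size of effect. The last matters most. Odds ratios and differences in proportion are linked, so one can ask whether any row available to 45–60 subjects is as strict as a bound of 1.6. None is.

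Fit is one of two hypotheses that must both succeed. If the two lenses fit equally well and precision is too low, the trial can miss its objective on fit for lack of information. A reader who takes 14.2 as the justification could then read that result as evidence of poorer fit.

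**Working it through.** **1. The plan's own table.** Power and the reference proportion are not visible, so 88/70/53/47 cannot be reproduced in a strict sense. Two-group and one-sample formulas with quite different assumed inputs all come within about 4% of the printed figures. The table is plausible, but its inputs cannot be recovered. The next two steps do not need them, because whatever was assumed is already in the printed numbers.

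**2. The margin as a difference in proportions.** Under a common odds ratio of 1.6, the largest possible gap in any cumulative proportion is

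(√1.6 − 1)/(√1.6 + 1) = 0.2649/2.2649 = 0.117,

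that is, 11.7 points, reached at 55.8% against 44.2%. Elsewhere it is smaller. From 80%, the odds are 4; 4/1.6 = 2.5; 2.5/3.5 = 71.4%; the gap is 8.6 points. In the same way it is 10.7 points from 70%, 5.1 from 90% and 2.8 from 95%.

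**3. Reading the table at that margin.** Only the 14% (53) and 15% (47) rows lie within 45–60 subjects, and both exceed 11.7 points. The 12% row needs 70 and the 10% row 88. Linear interpolation at 11.7% gives 70 + (12 − 11.7)/(12 − 10) × (88 − 70) = 72.7, about 73. This is the most lenient case, since 11.7 is a ceiling.

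**4. Power of the 14.5 test, per base curve.** Inputs:
- margin ln 1.6 = 0.470 (2.3)
- two-sided 95% limit, so z = 1.96 (14.5)
- correlation ρ = 0.5 (14.2)
- both lenses worn on the same eye, so N pairs per base curve (4.1)
- true odds ratio 1 (my assumption)

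Ordinal, proportional odds with a crossover factor: SE² = 6(1 − ρ)/[N(1 − Σp³)], power = Φ(0.470/SE − 1.96). Six equally used grades give 1 − Σp³ = 35/36, the largest value possible on a six-point scale, so this is the best case.
- N = 43: SE² = 3/41.81 = 0.0718; SE = 0.268; Φ(−0.21) = 42%.
- N = 60: SE² = 3/58.33 = 0.0514; SE = 0.227; Φ(0.11) = 54.5%, about 55%.
- For 80% power: N = 3 × (1.96 + 0.8416)²/(0.470² × 35/36) = 110. With a one-sided 5% limit instead, it is 87.

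Fit dichotomised: SE² = 2(1 − ρ)/(N p q). At p = 0.5 and N = 43, SE² = 1/10.75 and power is 34%; at N = 60 it is 44%. At p = 0.9 it is 15% and 19%.

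**5. Simulation check.** Paired grades, proportional-odds fit with robust standard errors, 400 runs per case (error about ±5 points). Five equal grades with observed correlation 0.49–0.50 gave 40% at 43 and 55% at 60.

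**6. Sensitivity.**

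| Change from the best case in step 4 | N = 43 | N = 60 |
|---|---|---|
| None (ρ = 0.5, evenly spread grades) | 42% | 55% |
| Grades split 5/15/40/40 | 38% | 50% |
| Grades split 10/80/10 | 24% | 31% |
| ρ = 0.7 | 62% | 76% |
| ρ = 0.8 | 79% | 91% |
| Base curves pooled (variance halved), ρ = 0.5 | 70% | 83% |
| True odds ratio that gives 80% power | about 0.75 | about 0.85 |

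In the last row, values below 1 favour Test under the upper-limit rule in 14.5.

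**The case against.** **The redaction.** The block that opens 14.2 stands where power, reference rate and assumed effect would normally appear, and what is redacted is not missing from the plan. This stands as a limit on the power figures. If the sponsor assumed a modest true advantage for Test, 43–60 subjects could be enough per base curve. It does not rescue the table: no hidden input makes a 14-point row as strict as a margin of at most 11.7 points.

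**The endpoint of the table.** No visible sentence ties the table to fit, and the other primary endpoint is itself a proportion of eyes. The column heading, which counts subjects by study arm, points towards a Test–Control comparison but does not settle the matter. So the statement that the table calls for more than 70 holds only if it is meant for fit. If it is meant for lens power, the visible text gives no basis for N on fit.

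**Correlation and pooling.** Power is acceptable or close to it at a correlation near 0.8 with well-spread grades, or with pooled base curves. That is true, but 14.2 states 0.5 and 14.5 compares by base curve.

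**Stronger readings that the documents do not support.**
- *That 43–60 subjects cannot support the fit test.* The sensitivity table and the redaction rule out so flat a claim.
- *That the test must pass in both base curves, so that power is lower still.* Section 2.3 requires both hypotheses, fit and lens power. Section 14.5 gives intervals by base curve but never says that both must pass.
- *That the table contains an arithmetic error.* Nothing shows this.

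**Conclusion.** The mismatch is established on the visible text and does not depend on hidden inputs: the bound of 1.6 is worth at most 11.7 points, and the rows within reach of 45–60 subjects are 14 and 15 points. The size of the power shortfall is conditional. With a true odds ratio of 1, an observed correlation of 0.5 and a separate test per base curve, best-case power is about 42% at 43 completers and 55% at 60. Against a conventional 80%, which is my assumption because the planned power is not visible, that is short by about 25 to 38 points. A higher correlation, pooling or a true advantage for Test would narrow or close the gap; clustered grades would widen it. The conclusion is that the plan does not visibly justify N for its fit hypothesis, not that the trial is bound to fail on it.

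**What to change.** In 14.2:
- Base the justification of N on the test in 14.5: log odds ratio, margin 1.6, within-eye crossover contrast, by base curve.
- State the power at 43 and 60 completers with the assumed grade distribution, true odds ratio and correlation, and show how it changes with the correlation.
- Say which endpoint the difference-in-proportion table serves, and do not present its 14–15% rows as the basis for the 1.6 margin.

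In 14.5, state whether non-inferiority on fit must hold in both base curves. If so, give the joint power in 14.2.

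The cost is a short calculation or simulation and some wording. Enrolment and procedures stay as they are. The price is a stated power that will probably look less favourable.
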